#### 7.1.3 Rules for Early Termination for Acute Toxicity.

- Bayesian probability calculations will be employed to define early termination rules for safety. The table below indicates termination rules after groups of patients have been treated, although the Bayesian probability of an event may be calculated at any time during the trial. Thousands of patients with certain types of cancer have undergone radiation therapy with protons. Thus, we will assume a modest amount of “prior” feasibility and safety data for protons delivered at the standard radiation dose for our Bayesian calculations. We will assume prior information equivalent to that of six treated patients, which is commonly required to establish safety in a standard 3+3 phase I trial design.
- Acute Toxicity. When examining the rate of acute toxicity from adjuvant radiation therapy in recent efficacy trials (4, 17), grade 3 acute toxicity differed between hematologic and non-hematologic (e.g. dyspepsia and nausea/vomiting) endpoints. In the MRC TE 18 trial, no patient experienced Grade 3 or higher thrombocytopenia, and Grade 3 dyspepsia was not reported. In the MRC TE 19 trial, <1% experienced Grade 3 or higher thrombocytopenia, and ~20% of patients experienced Grade 3 or higher Nausea/Vomiting. Because proton therapy is expected to spare normal tissues, an acute non-hematologic Grade 3 toxicity rate <20% is considered acceptable. We will assume a beta (1,5) prior, which is information equivalent to acute toxicity in one of six treated patients. If the number of patients with an acute toxicity is greater than or equal to the number in the table below, then termination will be considered, as it is likely that the toxicity rate is >20%, as noted by the Bayesian posterior probabilities.

We will monitor the number of patients with acute toxicity several times during the accrual phase.

Bayesian Rule for Acute Toxicity									
Patients treated and followed 90 days	3	6	12	18	24	30	36	42	48
Patients who experience acute toxicity	2	2	4	6	7	9	10	12	14
Posterior Prob[acute toxicity rate >20%]	0.80	0.62	0.76	0.84	0.79	0.85	0.82	0.87	0.91

Action	Terminate enrollment
--------	----------------------

#### 7.1.4 Statistical Analyses.

- Acute and Late Toxicity: All acute and late toxicities will be graded by CTC Version 4.0 and tabulated. Toxicity rates and 95% confidence intervals will be calculated.
- Analysis by Radiation Therapy Type: all subjects enrolled in this study will be followed and assessed for all endpoint analyses. However, a separate analysis may be performed for subjects who were treated with photon therapy as a portion of their planned course of radiation therapy.
- Moderate to Severe Lethargy: The 3-week rate and 95% CI will be computed. A one-sample one-sided chi-square test will be performed to test the null hypothesis that the lethargy rate is 35% (same as photon) versus the alternative hypothesis that the rate is reduced to 20%. Patients must have a minimum of 21 days of follow-up to be included. As a secondary analysis, the 3-week lethargy rate and 95% exact CI will be computed for each disease stage. A Fisher's exact test will be employed compare these rates, to determine whether lethargy rates significantly differ by disease stage.
- Clinical Efficacy: Time to local failure and time to distant failure will be estimated by the cumulative incidence method within a competing risks framework (competing risks are local failure, distant failure, death). Relapse-free survival, cause-specific survival, and overall survival will be estimated by the Kaplan-Meier method. Median values and 95% confidence intervals will be calculated.
- Quality of Life: Longitudinal quality of life measurements will be examined by plots of mean $\pm$  SD over time. Repeated measures ANOVA or linear mixed effects models (to assess the impact of fixed effects covariates), will be used to analyze the repeated observations. Piecewise linear models may be required to fit non-linear trends, as expected for the initial decline and then gradual increase in quality of life measures.

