#### 6.2.3

6.2.4 During Radiation Therapy: each patient will be assessed at least weekly during radiation therapy treatment. Each assessment will include a pertinent physical examination, performance status assessment (Appendix C), toxicity assessment (as per protocol section 6.2.5), laboratory evaluation to include complete blood count (optional), and quality of life assessment with EORTC QLQ-C30 (Appendix D), Testicular Cancer Patient Diary Card (Appendix E), and EuroQol EQ-5D (Appendix F).

6.2.5 Immediately Following Radiation Therapy: each patient will be assessed weekly for the first eight weeks following the completion of radiation therapy. Each assessment will include quality of life assessment with EORTC QLQ-C30 (Appendix D), Testicular Cancer Patient Diary Card (Appendix E), and EuroQol EQ-5D (Appendix F). At the discretion of the treating radiation oncologist, these weekly assessments may be performed in the physician clinic, via Internet-based surveys, via questionnaires from the patient home, or over the phone.

6.2.6 Toxicity Assessment: Patients will be treated and followed for a minimum of 90 days after the start of radiation treatment to determine safety (acute toxicity). The Common Toxicity Criteria v4.0 (Appendix A) [73] will be used to report acute adverse events that occur within 90 days of treatment initiation and late adverse events that occur after 90 days of protocol therapy initiation for up to 5 years.

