#### 7.1.2 Endpoints

- Acute Toxicity is defined as any Grade 3 or higher non-hematologic toxicity that occurs within 90 days following the start of proton therapy. NCI Common toxicity criteria (CTC Version 4.0) grades will be employed (Appendix A).
- Late Toxicity is defined as any Grade 3 or higher non-hematologic toxicity that occurs beyond 90 days following the start of proton therapy. NCI Common toxicity criteria (CTC Version 4.0) grades will be employed (Appendix A).
- Clinical Efficacy: Time to local failure will be defined as the time from the start of radiation therapy to local failure. Time to distant failure will be defined as the time from the start of radiation therapy to distant failure. Relapse-free survival will be defined from the time from the start of radiation therapy to any failure or death. Cause-specific survival will be defined from the time from the start of radiation therapy to death due to seminoma. Overall survival will be

defined from the time from the start of radiation therapy to death due to any cause or last patient follow-up. These outcomes will be summarized at the end of the phase II study.

- Quality of Life Measures: EORTC QLQ-C30, Testicular Cancer Patient Diary Card, and EuroQol EQ-5D will be evaluated at multiple times during and post-radiation. We hypothesize that compared to baseline, quality of life measures will worsen during and immediately post-radiation and will then gradually improve after radiation. These deficits are expected to be less than those seen for photon treated patients and the time course to return to baseline should be shortened. These outcomes will be summarized at the end of the phase II study.
- Moderate to Severe Lethargy will be scored on the Testicular Cancer Patient Diary Card (Appendix E). The rate of moderate to severe lethargy at week 3 will be evaluated. This outcome will be summarized at the end of the phase II study.

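### Late toxicity has no stated estimator, time horizon or data cut; if the planned rate is a simple proportion and is analysed before every patient has five years of follow-up, it understates the five-year risk

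*Combined protocol and SAP*

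**What the plan says.** The toxicity bullet of section 7.1.4 covers acute and late events together. They are to be graded and tabulated, and then "Toxicity rates and 95% confidence intervals will be calculated". It gives no denominator, time horizon, censoring rule or treatment of death for the late events.

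The endpoint in 7.1.2 is open-ended: "Late Toxicity is defined as any Grade 3 or higher non-hematologic toxicity that occurs beyond 90 days following the start of proton therapy". Section 6.2.6 sets the collection window, covering "late adverse events that occur after 90 days of protocol therapy initiation for up to 5 years". Section 6.2.7 adds enquiries about renal disease, cardiac disease and second malignancies in years 5 to 15.

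Section 3.1 plans 56 evaluable patients over 72 months, and 7.2 expects the whole trial to run for six years.

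Later in 7.1.4 the efficacy endpoints are handled differently: "Time to local failure and time to distant failure will be estimated by the cumulative incidence method within a competing risks framework". Also: "Relapse-free survival, cause-specific survival, and overall survival will be estimated by the Kaplan-Meier method".

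**The concern.** Acute toxicity has a window of the same length for every patient, and the monitoring table in 7.1.3 counts only patients followed for 90 days. A proportion is the natural summary there. Late toxicity has no such common window. Patients who entered recently, or who were lost, have had little time to show an event, yet a simple proportion keeps them in the denominator as if they were known to be event-free. The plan allows for unequal follow-up in failure and survival but makes no matching provision for late harm over the same period.

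Section 1.1 presents lower acute and late toxicity as the reason for studying protons, and objective 2.3.3 concerns late complications. A proportion read as a five-year risk would err in the direction that favours the study treatment.

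**Working it through.** **What rate means in this plan.** The documents give no figure for late toxicity to reproduce, so the meaning has to come from usage. In 7.1.3 the acute toxicity rate is a binomial proportion: "We will assume a beta (1,5) prior, which is information equivalent to acute toxicity in one of six treated patients". With x events in N patients the posterior is beta(1 + x, 5 + N − x). For 4 of 12 this is beta(5, 13), and Prob[rate > 20%] = 0.76, as the table states; all nine entries reproduce. The lethargy rate is also a proportion. Testing 35% against 20% gives n = [(1.645·√(0.35·0.65) + 0.842·√(0.20·0.80))/0.15]² = 55.87, hence the plan's 56.

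**Inputs from the documents.** Accrual over 72 months (3.1); late events from day 90, taken as 0.25 years, up to 5 years (6.2.6); trial length six years (7.2).

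**Assumptions.** Uniform accrual; true five-year late-toxicity risk of 10%; constant hazard from day 90; no deaths; data cuts at months 72, 84 and 96. The documents give none of these for late toxicity.

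**Follow-up at month 72.** It runs from 0 to 60 months with a median of 36. The fraction reaching five years is 1/6 = 17%, and the fraction not yet past day 90 is 0.25/6 = 4%.

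**Expected proportion.** The hazard is λ = −ln(0.90)/4.75 = 0.0222 per year. For a cut at T years, average 1 − exp(−λ·max(min(T − u, 5) − 0.25, 0)) over entry time u uniform on 0 to 6 years.

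- T = 6: (1/6)(0.10) + (1/6)[4.75 − 0.10/λ] = 0.0167 + 0.0403 = 0.0569
- T = 7: (2/6)(0.10) + (1/6)[4 − (e^(−0.75λ) − 0.90)/λ] = 0.0333 + 0.0392 = 0.0726
- T = 8: (3/6)(0.10) + (1/6)[3 − (e^(−1.75λ) − 0.90)/λ] = 0.0500 + 0.0347 = 0.0847

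| Data cut (assumed) | Expected proportion, true risk 10% |
|---|---|
| Month 72 | 5.7% |
| Month 84 | 7.3% |
| Month 96 | 8.5% |
| Month 132, all patients complete 5 years | 10.0% |
| Month 132, 2% per year loss | 9.5% |
| Month 132, 5% per year loss | 8.8% to 8.9% |

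The loss rows use λ/(λ + μ)·[1 − e^(−4.75(λ + μ))], with loss hazard μ = −ln(0.98) or −ln(0.95). If loss starts at treatment rather than at day 90, multiply by e^(−0.25μ). For 5% this gives 8.9% with loss from day 90 and 8.8% with loss from treatment.

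**Sensitivity.** By simulation at month 72, true risks of 5% and 20% give 2.8% and 11.4%, nearly the same relative shortfall. If the hazard rises over time (Weibull shape 2), a true 10% gives 4.4% at month 72 and 6.0% at month 84. Restricting the denominator to patients past day 90 changes 5.7% only to 5.9%.

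**The alternative estimator.** In 5,000 simulated trials of 56 patients cut at month 72, one minus Kaplan-Meier at five years averaged 10.1% for a true 10% and 19.7% for a true 20%. With no competing event this equals the cumulative incidence.

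**The case against.** A reader might infer that the plan commits itself to a biased late-harm estimate. The documents do not go that far, for three reasons.

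- Section 7.1.4 never says crude proportion. The usage in 7.1.3 concerns acute toxicity, and carrying it over to late toxicity is an inference. A person-time rate would not have this bias, though it would have to be named.
- No section names a five-year risk as the quantity to be estimated. A proportion reported with its follow-up is incomplete rather than wrong; it is biased low only when read as a fixed-period risk.
- No data cut is set. In 7.1.2 the efficacy, quality-of-life and lethargy outcomes are to be reported when the phase II study ends, but the two toxicity definitions carry no such statement. If the analysis waits for complete five-year follow-up, the bias is zero.

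A reader might also infer that progression ends toxicity follow-up. Section 8.4 points that way, ending adverse event collection when a patient goes off study at progression. Sections 3.6 and 5.2 call for toxicity and late effects to be followed afterwards. The documents conflict here, so loss at progression cannot be taken as given.

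Finally, the endpoint is secondary, with no threshold or test, and 8.2.1 describes most late effects as unlikely. In 56 patients, 5.7% against 10% is about 3 events against 6, and the exact 95% interval for 3/56 (1.1% to 14.9%) still contains 10%.

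All of this limits the certainty and weight of the point. It does not remove it: nothing in the plan requires waiting for complete follow-up, and the interval does not show the reader that its centre is shifted.

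**Conclusion.** The point holds conditionally. On the plan's own usage of rate, the late-toxicity summary is a proportion taken over unequal follow-up, and before all patients have five years it understates the five-year risk. The direction needs only that some patients have less than five years of observation. The size rests on the assumed 10% risk, hazard shape, accrual pattern and data cut: just over half the true value at month 72, about 85% of it at month 96, and no shortfall with complete follow-up. If everyone has had time to reach five years, what remains depends on an assumed loss rate and is modest. Because the estimator, horizon and data cut are all unstated, the text cannot support the flat claim that the late estimate will be biased. It does support the claim that 7.1.4 should name a method that accounts for follow-up, as it already does for failures. The sample size and the primary lethargy analysis are unaffected.

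**What to change.** In 7.1.4, separate the two analyses.

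- **Acute toxicity:** keep proportions, with exact (Clopper-Pearson) 95% intervals.
- **Late toxicity:** report the cumulative incidence of first Grade 3 or higher non-hematologic late toxicity among patients at risk at day 90, at stated times such as 2 and 5 years, with 95% intervals and numbers at risk. Treat death as a competing event and censor at the last toxicity assessment.
- **Data cut:** state it. At month 72 only about 9 of 56 patients (one sixth) would have reached five years, so a five-year estimate then would be imprecise.
- **Relapse and salvage therapy:** state how they enter the late-toxicity analysis, and reconcile 8.4 with 3.6 and 5.2, since these passages determine censoring.
- **Second malignancies and contralateral testicular tumours:** the same estimator can be used, though few events are expected by five years.

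The cost is analysis-plan wording and a few lines of code, with no additional patients, visits or data items. The downside is that late estimates will look less favourable and have wider intervals.

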# 1 Introduction

## 1.1 Background

Testicular cancers are the most common solid malignancies among men aged 20 to 35 years, with a projected 8,400 new cases of testicular malignancies in the United States annually (1). Approximately 60% of these malignancies represent pure seminomas, and 80% of patients diagnosed with seminoma have stage I disease (2-3). The standard initial treatment for stage I seminoma is radical inguinal orchietomy. Photon external beam radiation therapy has been standard adjuvant treatment and can achieve cause-specific survival rates approaching 100% and long-term relapse-free survival rates in excess of 95%, with virtually no relapses within the radiation portal (4-8).

However, radiation-induced treatment morbidities for seminoma have been reported. Acute toxicities are generally mild and self-limiting and include fatigue and gastrointestinal symptoms. Patients, however, are at an increased risk of late gonadal toxicity (9-11) and cardiovascular disease (12-14). Cardiac risks are higher among patients treated with mediastinal radiotherapy when compared to those treated with infradiaphragmatic radiation alone (12), patients receiving chemotherapy in addition to radiation therapy, and smokers (13, 15).

Following adjuvant radiation therapy, patients with seminoma are also at increased risks of contralateral testicular germ cell tumors in the first decade following adjuvant radiation therapy (16-18) and non-germ cell solid malignancies (RR = 2.0, 95% CI = 1.9-2.2) 10 to 35 years following radiation therapy (12-13, 15, 18-24). The risk of solid malignancies is higher for patients diagnosed with testicular cancers at younger ages. Based on tumor registry data, a patient diagnosed with a seminoma at age 35 years has a 36% risk of developing a second solid cancer within 40 years of his diagnosis, compared with 23% for the general population. As seminoma largely affects younger patients, and the cure rates from standard therapy are excellent, second primary cancers have emerged as a leading cause of death among survivors of testicular malignancies (12-13, 24).

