Despite reductions in radiation doses and treatment fields, surveillance has emerged as an alternative and increasingly utilized adjuvant course. Approximately 15% to 20% of unselected patients with stage I seminoma who undergo surveillance following orchiectomy develop disease recurrence (35-43). As greater than 80% of these relapses occur in the para-aortic lymph nodes, deferring immediate adjuvant therapy and administering chemotherapy or radiation therapy upon relapse allows for successful salvage therapy in most patients, with equivalent overall survival rates as for patients receiving immediate adjuvant therapy (41-43). However, treatment of patients undergoing surveillance who relapse is usually more intensive and associated with increased morbidity (44-45). More recently, groups have advocated a risk-adapted management strategy to guide adjuvant therapy (46). As the risk of relapse is higher in patients with tumor sizes great than 4 cm, rete testis invasion, or pT3 or pT4 disease, in the absence of a contraindication to adjuvant therapy, only patients with pT1 or pT2 histologies and smaller tumors who are committed to long-term follow-up are ideal candidates for surveillance (8, 33, 43, 46).

Short-course adjuvant carboplatin for one or two cycles has emerged as an alternative to adjuvant radiation therapy or surveillance (8, 47-48). An MRC and European Organization for Research and Treatment of Cancer trial (MRC/EORTC ISRCTN27163214) randomized 1,447 patients with pT1 to pT3 stage I seminoma to one course of carboplatin or adjuvant radiotherapy to 20 Gy to 30 Gy in 200 cGy daily fractions primarily to the para-aortic region (16-17). At a median follow-up of 6.5 yrs, there was no difference in 5-year relapse-free survival rates between the carboplatin arm and the radiation therapy arm (94.7% vs. 95.5%, HR 1.25, 90% CI 0.83 to 1.89). Patients in the carboplatin arm had higher rates of Grade 1 or Grade 2 thrombocytopenia (12% vs. 2%,  $p<0.0001$ ) and Grade 3 or Grade 4 thrombocytopenia (4% vs. 0%,  $p<0.0001$ ), whereas patients in the radiation therapy arm had higher rates of dyspepsia (17% vs. 8%,  $p<0.0001$ ) and a trend towards increased lethargy and time off of work in the acute setting. Additionally, fewer new contralateral testicular germ cell cancers were observed in the carboplatin arm (0.2% vs. 1.2%, HR 0.22,  $p=0.03$ ).

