reserved for salvage of patients who subsequently relapse. Contemporary studies in patients with IIA and nonbulky IIB seminoma have yielded five-year disease-free survival rates of 90 percent or higher.

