### **2.3 Phase II Secondary Objectives**

- 2.3.1 To evaluate the treatment efficacy of proton radiotherapy for all enrolled patients with seminoma as evidenced by time to local failure, time to distant failure, relapse-free survival, cause-specific survival, and overall survival, according to patient clinical stage and radiotherapy target volume treated.
- 2.3.2 To determine the incidence of additional acute toxicities of proton radiotherapy in patients with stage I, IIA, and IIB seminoma, including the incidence of hematologic toxicities, dyspepsia, and patients reporting being unable to perform normal work.
- 2.3.3 To assess late complications from irradiation to the para-aortic and pelvic regions using proton beam therapy, including late gonadal toxicity/spermatogenesis depression and the rates of contralateral testicular germ cell tumors, secondary solid cancers, and hematologic malignancies.
- 2.3.4 To compare the dose distribution to target volumes and surrounding normal structures using Dose Volume Histograms generated from proton plans used to treat study participants and photon plans that will be generated for comparison purposes.
- 2.3.5 To evaluate multiple domains of quality of life before, during, and after radiotherapy, including patient-reported assessments of lethargy, work or daily activity impairment, nausea/emeisis, change in bowel habits, mobility, self-care, pain/discomfort, anxiety/depression, and sleep.

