## 3 Subject Selection and Withdrawal

### **3.1 Accrual**

This study plans to enroll 56 evaluable patients over 72 months. The University of Pennsylvania, Penn satellites, Walter Reed National Military Medical Center, other affiliated Department of Defense (DOD) hospitals, and Massachusetts General Hospital (MGH), see in excess of 20 patients with stage I, IIA, and IIB testicular seminoma per year. Of the patients with seminoma treated annually at these participating institutions, we would reasonably expect to accrue 8 to 10 patients on study annually. Only MGH and the University of Pennsylvania will be treating patients with protons. The Walter Reed National Military Medical Center/Department of Defense affiliates will be referring patients to the University of Pennsylvania.

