## 6.2 Evaluation and Follow-up

6.2.1 Timing of Assessments: all subjects will be evaluated prior to initiation of treatment, weekly during the course of the primary protocol study treatment period and for eight weeks following the completion of proton beam radiation therapy, and 90 days following the start of radiation therapy by the treating radiation oncologist. Patients will be evaluated every three months during the first year following radiation therapy, approximately every six months during the second year following therapy, and annually for years three to five following therapy. Effort will be made to follow subjects beyond five years to assess for toxicity related to radiation treatment and survival, either by the treating radiation oncologist or a referring physician.

6.2.2 Pre-treatment: after determining eligibility, pre-treatment patient assessment will include history and physical examination, performance status assessment (Appendix C), toxicity assessment (as

per protocol section 6.2.5), and quality of life assessment with EORTC QLQ-C30 (Appendix D), Testicular Cancer Patient Diary Card (Appendix E), and EuroQol EQ-5D (Appendix F). Patients will also undergo pre-treatment laboratory evaluation to include complete blood count, semen analysis, follicle-stimulating hormone level, luteinizing hormone level, testosterone, and serum creatinine or creatinine clearance. **Patients who object to the semen analysis or are not covered by their insurance company to have the analysis will not be excluded from the study. If the semen analysis is performed, an optional DNA fragmentation will also be performed from the semen analysis if covered by the patients insurance. This portion of the analysis will only be performed at the Coordinating Center, University of Pennsylvania, and not at participating sites.**

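### Section 7.1.4 names only the median as numeric summary of the survival endpoints; at the protocol's own benchmarks it will almost surely not be reached, so 2- and 5-year estimates should be named

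*Combined protocol and SAP*

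**What the plan says.** Section 7.1.4 covers the three survival endpoints in two sentences: "Relapse-free survival, cause-specific survival, and overall survival will be estimated by the Kaplan-Meier method. Median values and 95% confidence intervals will be calculated". The median is the only point summary named. Section 7.1.2 defines the endpoints from the start of radiotherapy and promises a summary at the end of the phase II study. Objective 2.3.1 asks for the results "according to patient clinical stage and radiotherapy target volume treated". None of these places names a time at which survival will be reported.

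The benchmarks in the background are rates:
- Stage I after photon radiotherapy (section 1.1): "cause-specific survival rates approaching 100% and long-term relapse-free survival rates in excess of 95" per cent.
- Stage I, radiotherapy arm of the randomized comparison with carboplatin (section 1.1): 95.5% relapse-free at 5 years.
- Stage IIA and nonbulky IIB (section 1.2): "five-year disease-free survival rates of 90 percent or higher".

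On size and timing, section 3.1 states: "This study plans to enroll 56 evaluable patients over 72 months". Section 6.2.1 schedules visits to year 5 and adds: "Effort will be made to follow subjects beyond five years to assess for toxicity related to radiation treatment and survival". Section 3.6, in its text on withdrawn subjects, sets five years as the minimum for survival follow-up.

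**The concern.** A median survival time exists only once the estimated curve falls to 50%. With expected rates of 90% to above 95% at 5 years, that should not happen in a trial of this size and length. The planned summary would then carry no information about how well patients did. The benchmarks in sections 1.1 and 1.2 that carry a time are 5-year rates, so a median could not be compared with them even if one appeared. Because no time is fixed in advance, whoever writes the report would choose it after seeing the curve. This affects the efficacy part of objective 2.3.1, which is secondary and descriptive.

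**Working it through.** **The plan's own figure.** The plan gives no figure for the survival endpoints. The 56 comes from the lethargy test (sections 7.1.4 and 7.2: 35% versus 20%, one-sided 5%, 80% power): n = [1.645·√(0.35·0.65) + 0.842·√(0.20·0.80)]² / 0.15² = 55.9, so 56. Then 56/0.95 = 58.9, so 59 enrolled. Both figures reproduce.

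**Expected failures and implied medians.** S5 is the 5-year rate. Failures by 5 years are 56·(1 − S5). The constant-hazard median is 5·ln(0.5)/ln(S5).

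| S5 | Failures by 5 years | Implied median |
|---|---|---|
| 95.5% | 2.5 | 75 years |
| 95% | 2.8 | 68 years |
| 90% | 5.6 | 33 years |

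With complete follow-up, 28 failures are needed to bring the curve to 50%. The binomial chance of 28 or more by 5 years is at most 4·10⁻¹⁴, at S5 = 90%.

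**Staggered entry.** Simulation of 56 patients, 100,000 trials per scenario. Assumptions not in the documents: constant hazard −ln(S5)/5, uniform entry over 6 years, no loss to follow-up. Month 72 is the end of accrual; at month 132 the last patient has 5 years. Ranges run over the three values of S5.

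| Follow-up | Analysis | Median reached | Its lower 95% limit exists |
|---|---|---|---|
| Stops at 5 years | month 72 | under 0.01% | 1.5% to 4.2% |
| Stops at 5 years | month 132 | none | none |
| To analysis date | month 72 | 0.3% to 0.8% | 4.7% to 11.3% |
| To analysis date | month 132 | 0.3% to 1.1% | 4.5% to 15.1% |

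When patients are followed to the analysis date and a median does appear, in 72% to 99% of cases the curve crosses 50% with two or fewer patients at risk. In assumed subgroups of 28 or 14 patients, followed to the analysis date, the median is reached in 0.6% to 4.3% of trials.

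**Sensitivity.** With 5 years of follow-up each and 5% loss per year, the median was never reached. With 15 years each, it was reached in at most 0.02% of trials at the three benchmark rates. At S5 = 80%, below every benchmark, with follow-up stopped at 5 years, it was reached in 0.2% at month 72 and never with 5 years each. Only 80% combined with 15 years each makes it a real possibility (48%).

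**Overall and cause-specific survival.** Relapse-free survival counts every death (section 7.1.2), so overall survival cannot be lower. Cause-specific survival counts only seminoma deaths, and its benchmark is close to 100%. The conclusion carries over to both.

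**What fixed times would give.** With full 5-year follow-up and log-log 95% intervals:
- 3 failures in 56: 94.6% (84.3 to 98.2).
- 6 failures in 56: 89.3% (77.7 to 95.0).
- No failure in 56: 100%, one-sided exact lower 97.5% limit 0.025^(1/56) = 93.6%.

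At month 72, the number at risk at 2 years is 56·(4/6)·S(2), about 36. At 5 years it is 56·(1/6)·S5, about 9. The typical 5-year interval in trials with an event is 79% to 99% at S5 = 95% and 73% to 97% at 90%. Mean follow-up, stopped at 5 years, is (1·5 + 12.5)/6 = 2.92 years, or 163 person-years. At hazards of 0.0092 (95.5%) and 0.0103 (95%) that is about 1.5 and 1.7 failures. No failure at all then has probability of about e^−1.5 = 22% and e^−1.7, close to 19%.

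**The case against.** The strongest reply is that little is lost. Kaplan-Meier curves are planned, a 5-year value can be read from them, and the promised confidence intervals may be meant for the curve as well as the median. *Not reached* would be a correct report. Section 7.1.4 also plans cumulative incidence of local and distant failure with death competing. If these are analysed as first events, the three curves add to one minus relapse-free survival. No test, power or decision depends on these endpoints.

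Most of this stands and limits the weight of the point. It does not remove it: no reporting time is named for the curve or for the cumulative incidence, and the one summary that is named will almost surely be empty.

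Two stronger readings are tempting. A reader might infer that the survival endpoints cannot be estimated. The documents do not support that, because the curves are planned and estimable. A reader might also infer from "Toxicity rates and 95% confidence intervals will be calculated" that late toxicity will be a crude proportion over unequal follow-up and so be understated. The documents do not choose a crude proportion and give no late-toxicity risk from which to size an error, and section 6.2.6 sets a window of up to 5 years. That line does not support a criticism here.

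Nor is a 5-year estimate a cure at any cut-off. At month 72 the intervals for true rates of 95% and 90% overlap almost completely.

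**Conclusion.** The point holds as a defect in the choice of summary. At the protocol's benchmarks the median of relapse-free survival is reached in about 1% of trials or fewer, and in essentially none if follow-up stops at 5 years. Overall and cause-specific survival are no more likely to reach it. This rests on 56 patients, constant hazard, uniform 6-year entry and no loss to follow-up. The margin is wide enough that moderate departures would not change it. It should be corrected, because a better summary is nearly free and matches the 5-year benchmarks. The primary lethargy analysis, the sample size and the acute-toxicity stopping rule are unaffected.

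**What to change.** In section 7.1.4, replace the sentence on medians with text to this effect: relapse-free, cause-specific and overall survival will be reported as Kaplan-Meier estimates at 2 and 5 years with 95% confidence intervals and numbers at risk, overall and by clinical stage and target volume; the median will be reported only if reached.

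Add three short statements:
- The data cut-off date.
- The 5-year estimate is treated as mature only once patients have completed their 5-year follow-up. Any earlier 5-year figure is labelled as imprecise and shown with its number at risk.
- Where no event has occurred, the usual log-log interval is undefined. Give the number at risk and a one-sided exact lower limit, 0.025^(1/m), where m is the number of patients with complete follow-up to that time. This is 93.6% for m = 56 but only about 66% for m = 9, so the limit for 56 must not be quoted at an early cut-off.

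The cost is a short paragraph in 7.1.4, using data already collected. Sample size, visits and the primary analysis do not change.
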